10.4.2 Key Efficacy Analysis

Comparisons between the MD-7246 dose groups and placebo with regard to the change from baseline in abdominal pain over the Treatment Period will be evaluated employing a MMRM framework with week (categorical), treatment, geographic region, and week-by-treatment fixed effects, patient as the random effect, and baseline value as a covariate. An unstructured covariance structure will be utilized. Descriptive statistics, for the overall Treatment Period effect, based on the MMRM model will include least-squares (LS) mean change from baseline for each treatment, the LS mean difference between each MD-7246 dose and placebo, corresponding 95% CIs, and the p-value associated with the comparison. In addition, weekly treatment differences between each MD-7246 group and placebo will be provided using the same MMRM model defined above.

For the 6/12 Week Abdominal Pain 30% Responder endpoint, the proportion of responders in each MD-7246 group will be compared to the proportion of responders in the placebo group using a Cochran-Mantel-Haenszel (CMH) test controlling for geographic region. The number and percent of responders, the difference in responder rates between each MD-7246 group and the placebo group, the odds ratio relative to placebo, all corresponding 95% CIs, and the p-value associated with the CMH test will be presented.

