7.8.9.1. Key Efficacy Endpoints

Change from Baseline in Abdominal Pain Through the Treatment Period

The Change from Baseline in Abdominal Pain Through the Treatment Period is defined as the overall change from baseline in the Abdominal Pain through the Treatment Period, which is estimated based on each weekly change from baseline in the abdominal pain score (based on the daily abdominal pain at its worst score) minus the baseline abdominal pain score for patients in the mITT population.

The postbaseline weekly abdominal pain score is the average of the non-missing daily abdominal pain at its worst scores during a week (Weeks 1-12) if there are at least 4 daily scores entered into the eDairy during the week, or will be considered as missing if there are less than 4 daily scores in the week. Weekly change from baseline will be calculated for each week as the weekly score minus the baseline score.

6/12 Week Abdominal Pain 30% Responder

The 6/12 Week Abdominal Pain 30% Responder is defined for patients in the mITT population and is a patient who meets the Weekly Abdominal Pain 30% Responder criteria for at least 6 out of the 12 weeks of the Treatment Period. A Weekly Abdominal Pain 30% Responder is a patient who has a decrease from baseline of at least 30% in the weekly abdominal pain for that week. If a patient did not have an abdominal pain score for at least 4 days in a particular week during the Treatment Period, the patient will not be considered a Weekly Abdominal Pain 30% Responder for that week. For all weeks after the treatment discontinuation, the patient will be considered as non-responder. A patient in mITT population who did not have any post baseline assessment for abdominal pain at its worst will be considered a weekly non-responder for all post baseline weeks, subsequently, will not be a 6/12 week abdominal pain responder.

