7.8.9.2. Analyses of the Key Efficacy Endpoints

Change from Baseline in Abdominal Pain Through the Treatment Period

The overall treatment effect will be evaluated via the comparison between the MD-7246 dose groups and placebo with regard to the weekly change from baseline (CFB) in abdominal pain using a MMRM model, including the weekly CFB score in abdominal pain as dependent variable and treatment, visit week (categorical), and treatment-by-week as fixed effects, patient as a random effect, and the baseline value as a continuous covariate. An unstructured covariance matrix will be used for the MMRM analysis, unless the model does not converge, in which case the compound symmetry will be used.

In this MMRM, a patient in mITT population without any postbaseline abdominal pain score at its worse will be considered missing. For patients with postbaseline abdominal pain scores, at any particular week, if there are fewer than 4 daily scores available, the weekly change from baseline will be considered as missing. Weeks after the treatment discontinuation will be considered as missing.

Descriptive statistics for the overall treatment effect based on the MMRM model will include the least-squares (LS) mean difference between each MD-7246 dose and placebo, LS mean change from baseline for each treatment, their corresponding 95% CIs, and the p-values associated with the comparisons to placebo. In addition, LS Means for the weekly treatment differences between each MD-7246 group and placebo will also be provided with the same set of statistics derived from the same MMRM model defined above and will be plotted based on the MMRM estimates.

Additionally, the non-model based descriptive statistics for the corresponding change from baseline (overall or weekly) will be provided by treatment group in the same tables for the MMRM estimates. Among them, the overall change from baseline is defined as the average of all non-missing post baseline daily scores during the Treatment Period minus the baseline abdominal pain score. The cumulative distribution for the overall change from baseline during the entire treatment period will be summarized and plotted by treatment group.

6/12 Week Abdominal Pain 30% Responder

For the 6/12 Week Abdominal Pain 30% Responder endpoint, the proportion of responders in each MD-7246 treatment group will be summarized and compared to the proportion of responders in the placebo group using a CMH test. The number and percentage of responders,

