7.8.9.4. Additional Efficacy Endpoints and Analyses

The following endpoints are defined similarly to the Change from Baseline in Abdominal pain, for its overall and weekly. They will be analyzed using similar MMRM model and the non-model based summary statistics for the Change from Baseline in Abdominal Pain (through the Treatment Period and at each week):

- Change from Baseline in Abdominal Discomfort through the Treatment Period and at each week
- Change from Baseline in Abdominal Bloating through the Treatment Period and at each week
- Change from Baseline in Abdominal Cramping through the Treatment Period and at each week
- Treatment Satisfaction through Treatment period and at each week will be summarized and analyzed using MMRM model (without baseline in the model). Treatment Satisfaction is scored weekly on a 5-point scale during the Treatment Period only and no change from baseline is defined for this assessment.

The following 6/12 week responder endpoints are defined in the same manner as the 6/12 Week Abdominal Pain 30% Responder based on their relevant weekly responders. For each week in the Treatment Period, a weekly responder is a patient who satisfies the responder criteria in the change from baseline for that week. If a patient did not enter information into the eDiary on at least 4 days for a particular week during the Treatment Period, the patient will not be considered a weekly responder for that week. A patient who did not have any relevant post baseline assessment will be considered a weekly non-responder for all post baseline weeks, subsequently, will not be a 6/12 week responder. For all weeks after the treatment discontinuation, the patient will be considered as non-responder.

These responder endpoints will be summarized by treatment and the comparison between the active treatment group and placebo will be analyzed using a CMH test. The relevant number and percentage of weekly responders will be summarized by treatment at each week.

- 6/12 Week Abdominal Pain 40% Responder
A 6/12 Week Abdominal Pain 40% Responder is a patient who meets the Weekly Abdominal Pain 40% Responder criteria for at least 6 out of the 12 weeks of the Treatment Period.
- 6/12 Week Abdominal Pain 50% Responder
A 6/12 Week Abdominal Pain 50% Responder is a patient who meets the Weekly Abdominal Pain 50% Responder criteria for at least 6 out of the 12 weeks of the Treatment Period.
- 9/12 Week Abdominal Pain 30% Sustained Responder

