APPENDIX 1. CHANGES FROM ANALYSES PLANNED IN THE PROTOCOL

Type	Protocol	SAP	Justifications
Language Clarification	Change from baseline at Each Week in various efficacy assessments	Change from baseline through the Treatment Period and at Each Week	To differentiate 
 • Change through the entire Treatment Period. • Individual weekly changes
	Treatment Period was used for 2 periods: 
 • From the day of the first dose to 1 day after the last dose • From the day of the first dose to the day of the last dose 	Clearly distinguish different periods: 
 • From the day of the first dose to 1 day after the last dose is defined as Treatment Emergent Period. • From the day of the first dose to the day of the last dose is defined as Treatment Period. 	Clarification
Operational Adjustment	
 • An optional interim analysis of unblinded safety and efficacy data may be performed to assess futility. • Sensitivity analyses planned for the change from baseline in abdominal pain score • Analyses for Health outcome parameters SF-12v2 and EQ-5D-3L were included. 	
 • No interim analysis performed • No sensitivity analysis performed • Analyses for Health outcome parameters SF-12v2 and EQ-5D-3L will be in a separate analysis plan. 	
 • Faster enrollment won't leave time for an interim analysis. • In a hypothesis generating phase 2 study, the sensitivity analysis is unnecessary. • HEOR parameters will be detailed out in relevant analysis plan

Type	Protocol	SAP	Justifications

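### If the unstructured MMRM fails to converge, the SAP falls back to compound symmetry with no robust standard errors specified, so weekly CIs and p-values can be wrong; the key overall contrast stays close to nominal

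*SAP*

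**What the plan says.** Protocol 10.4.2 specifies one structure and no fallback: "An unstructured covariance structure will be utilized". SAP 7.8.9.2 keeps the unstructured matrix and adds a rule: "unless the model does not converge, in which case the compound symmetry will be used". SAP Appendix 1, which lists departures from the protocol's analyses, does not mention this addition. Neither document names an intermediate structure, a robust standard error or a degrees-of-freedom method.

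The same model supplies the week-by-week results: "LS Means for the weekly treatment differences between each MD-7246 group and placebo will also be provided with the same set of statistics". That set includes 95% CIs and p-values.

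Three other statements limit the weight of the point:
- The key continuous endpoint in SAP 7.8.9.1 is "defined as the overall change from baseline in the Abdominal Pain through the Treatment Period", not the change at any one week.
- SAP 7.8.9.2 also promises that "the non-model based descriptive statistics for the corresponding change from baseline (overall or weekly) will be provided by treatment group", in the same tables as the model estimates.
- SAP Appendix 1 describes the study's purpose in dropping sensitivity analyses: "In a hypothesis generating phase 2 study, the sensitivity analysis is unnecessary".

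For discomfort, bloating and cramping, SAP 7.8.9.4 says "They will be analyzed using similar MMRM model and the non-model based summary statistics". It does not say whether the fallback carries over.

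**The concern.** An unstructured matrix for 12 weeks has 78 parameters: 12 variances and 66 covariances. Compound symmetry has two. The rule goes from one to the other in a single step.

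Under compound symmetry with complete data, every week receives the same pooled variance. A week whose true variance is above the pool gets an interval that is too narrow and a p-value that is too small. A week below the pool gets the reverse. With dropout there is a second route. If correlation falls with lag, a constant correlation credits the early weeks with too much information about the late ones, so late-week standard errors are too small even when the variances are equal.

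What is at stake is the weekly dose-versus-placebo results. They include Week 12, the time point on which SAP Section 4 sizes the study. SAP 7.8.9.3 plans no sensitivity analysis of the key endpoints, so no second model would expose a poor covariance choice.

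**Working it through.** **The plan's own figure.** SAP Section 4 uses a difference of 1.0, SD 2.4, 92 per arm and two-sided 0.05. The standard error is 2.4 × √(2/92) = 0.354, so the noncentrality is 1.0/0.354 = 2.83. Noncentral-t power on 182 degrees of freedom is 80.3%, which agrees with the stated 80%.

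**Inputs.** From the documents: 12 weekly scores, 92 per arm, two-sided 5%, and a Week 12 SD of 2.4 (range 2.32 to 2.88 in the earlier Phase 2b trial). Assumed, because the documents do not give them: SDs at other weeks, between-week correlations and the dropout rate.

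**Weekly contrasts, complete data.** Pooled SD = √(mean of the 12 weekly variances). For week t, ratio = pooled SD / SD_t and error = 2 × [1 − Φ(1.96 × ratio)].

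Worked case, SD rising linearly from 1.6 to 2.4:
- The mean variance is 4.063, so the pooled SD is 2.016.
- Week 12: ratio 2.016/2.4 = 0.840, error 2 × [1 − Φ(1.646)] = 9.97%.
- Week 1: ratio 2.016/1.6 = 1.260, error 2 × [1 − Φ(2.469)] = 1.35%.
- Week 12 half-width, 1.96 × SD × √(2/92): 0.58 reported against 0.69 true.

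| Assumed SD path | Week 12 error, % | Week 1 error, % |
|---|---|---|
| Linear from 2.0 / 1.8 / 1.6 / 1.4 to 2.4 | 7.2 / 8.5 / 10.0 / 11.6 | 3.1 / 2.2 / 1.4 / 0.7 |
| Same starts, rising over Weeks 1–4, then flat at 2.4 | 5.63 / 5.95 / 6.25 / 6.54 | 2.20 / 1.20 / 0.52 / 0.16 |
| Falling linearly from 2.8 to 2.4 | 3.35 | 6.84 |
| Constant | 5.0 | 5.0 |

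On the early-plateau path from 1.6, the Week 12 half-width is 0.66 reported against 0.69 true.

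**Overall contrast, complete data.** The variance of a patient's 12-week mean is (mean variance + 11 × mean covariance)/12. Compound symmetry estimates exactly those two means, so the overall standard error is right whatever the true pattern.

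**With dropout, by simulation.** There were 4 arms of 92, a baseline covariate and a REML fit. Nominal error is 5%, and Monte Carlo error is about 0.6 to 1.1 points.
- SD linear from 1.6 to 2.4 with about 20% dropout: compound-symmetry Week 12 error was between 10.8% and 11.8% across separate runs. On the early-plateau path it was 6.5%.
- Constant SD, correlation decaying with lag, 15–30% dropout: Week 12 error was 5.5–6.9%. Unequal variances are therefore not the only route.
- Overall contrast: about 5.1–6.1% with 20–30% dropout. The largest value found was 6.7%, at 30% dropout with the SD doubling over the 12 weeks.

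**With sandwich errors.** In one simulation (1,500 runs per scenario, linear 1.6 to 2.4), compound symmetry behaved as follows:
- Without dropout, Week 12 error fell from 9.8% to 5.4% and Week 1 rose from 1.1% to 4.7%.
- With 20% dropout, Week 12 fell from 10.8% to 5.5% and Week 1 rose from 1.4% to 5.3%. The overall contrast hardly moved (4.5% to 4.0%).

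A second simulation covered three settings. With sandwich errors, Week 12 error was 4.7–5.3% for compound symmetry and 4.3–5.0% for heterogeneous Toeplitz.

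**How often the branch is reached.** The unstructured model converged in 1,200 of 1,200 simulated trials. Those data were Gaussian with no intermittent missing weeks, and the code was not SAS, so this suggests the branch is unlikely but does not prove it.

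**The case against.** The strongest reply is that harm needs two things together: a failed unstructured fit and a covariance far from compound symmetry. Nothing in the documents suggests the first, and 368 patients is a reasonable number for 78 covariance parameters. The size of the second is assumed, and even its direction is unknown: a falling SD makes Week 12 conservative. The key contrast is protected, there is no multiplicity control (SAP 7.6), and the descriptive SDs would reveal unequal variances. All of this stands and sets the weight. It does not make the rule sound once triggered, since descriptive SDs do not repair the intervals.

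A reader might infer more than the documents support:
- *That the key efficacy test is invalid.* It is the overall Treatment Period contrast, which is exact with complete data and near nominal with dropout.
- *That the Week 12 test carries inflated error as planned.* Only the fallback has this problem. Week 12 is the sizing time point, not the key tested contrast.
- *That the SAP rejects robust standard errors.* It is silent on them.
- *That the model is over-specified,* because it lists "treatment-by-week as fixed effects, patient as a random effect, and the baseline value as a continuous covariate" alongside an unstructured matrix. The ordinary reading is patient as the repeated-measures subject, and no effect of the wording on results was shown.
- *That one particular sequence of structures is required.* The structured fits were not tested after a failed unstructured fit, so any order is a preference.

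**Conclusion.** The point holds, conditionally. If compound symmetry is used with model-based standard errors, the weekly CIs and p-values are unreliable when variances differ by week, or when correlation decays with lag and patients drop out. Week 12 error could plausibly lie anywhere from about 3% to 12%, and which end applies depends on SD paths that the documents do not give. The overall contrast stays at about 5–6% in realistic dropout settings. Because the branch is unlikely and no stated decision depends on a weekly p-value, the change is optional. It is still worth making before unblinding, since it is cheap and avoids choosing a standard-error method after seeing a failed fit.

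**What to change.** Amend the fallback sentence in SAP 7.8.9.2 to say that, whenever a structure other than unstructured is used, empirical (sandwich) standard errors with compatible degrees of freedom (for example between-within) will be used, and that the structure used will be reported for each endpoint. Reporting by endpoint also settles what happens for discomfort, bloating and cramping.

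Trying a heterogeneous structure, such as heterogeneous Toeplitz, before compound symmetry is a reasonable optional addition.

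The cost is one sentence and slightly more programming. There are two limits. The simulations used a fixed critical value of about 1.97 to 1.98 for the sandwich tests, not between-within degrees of freedom. And sandwich errors correct the standard error but not any bias from a misspecified covariance under missing-at-random dropout. When simulated dropout depended on earlier scores in opposite directions by arm, compound symmetry shifted the overall difference by 0.02–0.05 and the Week 12 difference by 0.07–0.10. That bias is the reason to prefer a richer structure where one converges.

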7.8.9.3. Sensitivity Analyses of the Key Efficacy Endpoints

No sensitivity analysis analyses for the two key efficacy endpoints will be performed.

7.8.9.4. Additional Efficacy Endpoints and Analyses

The following endpoints are defined similarly to the Change from Baseline in Abdominal pain, for its overall and weekly. They will be analyzed using similar MMRM model and the non-model based summary statistics for the Change from Baseline in Abdominal Pain (through the Treatment Period and at each week):

- Change from Baseline in Abdominal Discomfort through the Treatment Period and at each week
- Change from Baseline in Abdominal Bloating through the Treatment Period and at each week
- Change from Baseline in Abdominal Cramping through the Treatment Period and at each week
- Treatment Satisfaction through Treatment period and at each week will be summarized and analyzed using MMRM model (without baseline in the model). Treatment Satisfaction is scored weekly on a 5-point scale during the Treatment Period only and no change from baseline is defined for this assessment.

The following 6/12 week responder endpoints are defined in the same manner as the 6/12 Week Abdominal Pain 30% Responder based on their relevant weekly responders. For each week in the Treatment Period, a weekly responder is a patient who satisfies the responder criteria in the change from baseline for that week. If a patient did not enter information into the eDiary on at least 4 days for a particular week during the Treatment Period, the patient will not be considered a weekly responder for that week. A patient who did not have any relevant post baseline assessment will be considered a weekly non-responder for all post baseline weeks, subsequently, will not be a 6/12 week responder. For all weeks after the treatment discontinuation, the patient will be considered as non-responder.

These responder endpoints will be summarized by treatment and the comparison between the active treatment group and placebo will be analyzed using a CMH test. The relevant number and percentage of weekly responders will be summarized by treatment at each week.

- 6/12 Week Abdominal Pain 40% Responder
A 6/12 Week Abdominal Pain 40% Responder is a patient who meets the Weekly Abdominal Pain 40% Responder criteria for at least 6 out of the 12 weeks of the Treatment Period.
- 6/12 Week Abdominal Pain 50% Responder
A 6/12 Week Abdominal Pain 50% Responder is a patient who meets the Weekly Abdominal Pain 50% Responder criteria for at least 6 out of the 12 weeks of the Treatment Period.
- 9/12 Week Abdominal Pain 30% Sustained Responder
A 9/12 Week Abdominal Pain Sustained Responder is a patient who meets the Weekly Abdominal Pain 30% Responder criteria for at least 9 out of the 12 weeks of the Treatment Period.
- 9/12 Week Abdominal Pain 50% Sustained Responder
A 9/12 Week Abdominal Pain Sustained Responder is a patient who meets the Weekly Abdominal Pain 50% Responder criteria for at least 9 out of the 12 weeks of the Treatment Period.
- 6/12 Week Abdominal Discomfort 30% Responder
A 6/12 Week Abdominal Discomfort 30% Responder is a patient who meets the Weekly Abdominal Discomfort 30% Responder criteria for at least 6 out of the 12 weeks of the Treatment Period.
- 6/12 Week Abdominal Bloating 30% Responder
A 6/12 Week Abdominal Bloating 30% Responder is a patient who meets the Weekly Abdominal Bloating 30% Responder criteria for at least 6 out of the 12 weeks of the Treatment Period.
- 6/12 Week Abdominal Cramping 30% Responder
A 6/12 Week Abdominal Cramping 30% Responder is a patient who meets the Weekly Abdominal Cramping 30% Responder criteria for at least 6 out of the 12 weeks of the Treatment Period.
- 6/12 Week Degree of Relief Responder
A 6/12 Week Degree of Relief Responder is a patient who scores ≤ 2 for at least 6 out of the 12 weeks of the Treatment Period.
- 6/12 Week Adequate Relief of IBS Pain Responder

A 6/12 Week Adequate Relief of IBS Pain Responder is a patient who reports adequate relief of IBS pain (“yes”) for at least 6 out of the 12 weeks of the Treatment Period.

The following responder endpoints are defined based on whether a patient satisfies certain criteria for the change from baseline in daily abdominal pain at its worst on at least 50% of protocol defined treatment days (84 days). If a patient did not enter information into the eDiary on at least 42 days during Treatment Period, the patient will not be considered a responder for any of the following responder endpoints. Numbers and percentages of patients satisfying these responder definitions will be summarized by treatment and the comparison between each active treatment group and placebo will be analyzed using a CMH test.

- 50% of Days Daily Abdominal Pain 30% Responder

A 50% of days Daily Abdominal Pain 30% Responder is defined as a patient who achieves at least 30% decrease from baseline in daily abdominal pain score at its worst for at least 50% of days in the 12-week Treatment Period, which is at least 42 days. These 50% days with at least 30% decrease don’t have to be consecutive during treatment period.

- 50% of Days Daily Abdominal Pain 40% Responder

A 50% of days Daily Abdominal Pain 40% Responder is defined as a patient who achieves at least 40% decrease from baseline in daily abdominal pain score at its worst for at least 50% of days in the 12-week Treatment Period, which is at least 42 days. These 50% days with at least 40% decrease don’t have to be consecutive during the Treatment Period.

- 50% of Days Daily Abdominal Pain 50% Responder

A 50% of days Daily Abdominal Pain 50% Responder is defined as a patient who achieves at least 50% decrease from baseline in daily abdominal pain score at its worst for at least 50% of days in the 12-week Treatment Period, which is at least 42 days. These 50% days with at least 50% decrease don’t have to be consecutive during the Treatment Period.

Additionally, the cumulative distribution of patients satisfying 50% of days daily abdominal pain response based on the percent change from baseline will be plotted and tabulated by treatment group and by percent change from baseline in the daily abdominal pain at its worst.

Abdominal pain is measured daily using an 11-point NRS. Abdominal pain-free days will be those days where the patient reports a score of 0 for abdominal pain at its worst. The post baseline number of abdominal pain-free days per week will be calculated as the number of Abdominal Pain-free Days during the Treatment Period (from the first to the last dose), divided by the total number of days within Treatment Period times 7. The baseline percent number of abdominal pain-free days per week will be calculated as the number of Abdominal Pain-free Days during the Pretreatment Period (per defined Pretreatment Period), divided by the total number of days within the Pretreatment Period times 7. The descriptive statistics (n, mean, SD, median, minimum and maximum) for the baseline and post-baseline abdominal pain-free days

per week and the count of abdominal pain-free days during the Treatment Period will be tabulated by treatment group.

Assuming the count for the abdominal pain free days follows a Poisson distribution, the post-baseline abdominal pain-free days will be analyzed using a Poisson regression with treatment and baseline number of abdominal-pain free days as the covariates along with an offset variable of treatment duration (in weeks). In the case of overdispersion, the negative binomial model instead of Poisson regression will be implemented. Model estimates for weekly abdominal pain free days will be presented by treatment along with corresponding 95% confidence intervals. In the same table, the difference between the weekly rates for MD-7246 treatment arms and placebo will be represented with corresponding 95% confidence intervals and p-values associated with the comparisons to placebo.

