Patient assessment of adequate relief of IBS pain will be reported weekly by eDiary entry. The rating of adequate relief during the previous 7 days on a binary scale will be provided by the patient answering the following question:

“Overall, have you had adequate relief from your IBS pain during the past 7 days?”

1=Yes

2=No

Weekly Patient Assessment of Treatment Satisfaction

Patient assessment of treatment satisfaction will be reported weekly by eDiary entry each week of the Treatment Period after the Randomization Visit. Patients will answer the following question on a 5-point ordinal scale:

“Overall, how satisfied are you with the study medication’s ability to relieve your IBS symptoms?”

1=Not at all satisfied

2=A little satisfied

3=Moderately satisfied

4=Quite satisfied

5=Very satisfied

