7.3. Handling of Dropouts/Missing Data Imputation Method

For weekly responder endpoints based on daily eDiary entries (eg, Weekly Abdominal Pain 30% Responder), a patient who reported daily assess for fewer than 4 days during a week within the Treatment Period will be considered a non-responder for that week. A patient will be deemed a weekly non-responder for all weeks following the patient's discontinuation from the study treatment.

Similarly, the weekly symptom score that is calculated using daily eDiary symptom assessments will be the average of available daily assessment records for at least 4/7 records during the relevant week. The weekly symptom score will be set to missing for weeks with fewer than 4 days of daily assessments. For patients who prematurely discontinues the treatment prior to Week 12, the weekly symptom scores will be considered missing for all weeks after the treatment discontinuation.

Unless stated otherwise, missing data will not be imputed.

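### SAP 7.8.9.4 applies the 4-eDiary-day rule to two responder endpoints defined by a single weekly answer, so a recorded favourable answer can be counted as non-response

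*SAP*

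**What the plan says.** **SAP 7.8.9.4.** One paragraph governs the whole list of weekly-based responders. It begins "The following 6/12 week responder endpoints are defined in the same manner as the 6/12 Week Abdominal Pain 30% Responder". Its missing-data condition reads "If a patient did not enter information into the eDiary on at least 4 days for a particular week during the Treatment Period", and the consequence is that the patient is not a weekly responder for that week. No listed endpoint is exempted. Two entries rest on weekly questions: "A 6/12 Week Degree of Relief Responder is a patient who scores ≤ 2 for at least 6 out of the 12 weeks" and "A 6/12 Week Adequate Relief of IBS Pain Responder is a patient who reports adequate relief of IBS pain".

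**SAP 7.3.** The same 4-day minimum is introduced with a narrower scope: "For weekly responder endpoints based on daily eDiary entries (eg, Weekly Abdominal Pain 30% Responder"). The section ends with a default: "Unless stated otherwise, missing data will not be imputed".

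**SAP 5.3.2.** "Patient assessment of adequate relief of IBS pain will be reported weekly by eDiary entry", as a single yes/no answer about the past 7 days. Degree of Relief is likewise one weekly answer, on a 7-point scale. The protocol synopsis (Study Procedures, Weekly Assessments) has both answered once a week alongside an evening report.

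**Protocol 10.4.3.** The 4-day rule is attached to the abdominal pain 50% responder and carries over to discomfort, bloating and cramping by reference to the pain criteria. The Degree of Relief and Adequate Relief definitions have no diary-day condition.

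**SAP Appendix 1** does not list an extension of the rule to these two endpoints. **SAP Appendix Table 3-2** gives weekly questions their own validity rule: an answer belongs to the analysis week of which its recall covers at least 4 days.

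**The concern.** The 4-day minimum makes sense where a weekly score is averaged from daily ratings, because a mean of one or two days represents the week poorly. Degree of Relief and Adequate Relief involve no averaging. One completed evening report is enough to give the full weekly datum. Applying the minimum to them discards an observed answer because of gaps elsewhere in the diary.

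The SAP is also inconsistent about scope. A programmer working from 7.3 would leave these endpoints alone; one working from 7.8.9.4 would overwrite answers. Since Appendix 1 is silent, a reader of the results could not tell that the definition differs from the protocol's. At stake are the responder rates, and possibly the between-arm contrasts, for two patient-reported relief endpoints in a dose-finding trial.

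**Working it through.** **1. The plan's own figure.** The plan gives no number for this issue. Its only related figure is the power for the key endpoint: 1.0 / (2.4 × √(2/92)) = 2.826, and Φ(2.826 − 1.960) = 0.807 (0.803 with the t distribution, 182 df), against a stated value of about 80%. It reproduces and does not depend on this point.

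**2. A case that needs no model.** A patient reports adequate relief in exactly 6 of 12 weeks; in one of those weeks only 3 days have eDiary information.
- Protocol 10.4.3: 6 of 12, responder.
- SAP 7.8.9.4: 6 − 1 = 5 of 12, non-responder.

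The same holds for a Degree of Relief score of 2 or less.

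**3. Illustrative size.** The documents give neither the weekly response probability *p* nor the daily completion probability *c*. Both are assumed here, with days and weeks independent and only evening reports counted as diary days.

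Given that the weekly question was answered, one report exists that week. The week is overwritten if at most 2 of the other 6 days have a report:

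*q* = P(Bin(6, *c*) ≤ 2)

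At *c* = 0.8: 0.000064 + 0.001536 + 0.01536 = 0.017.

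The 6/12 rate is P(Bin(12, *p*) ≥ 6) without the rule and P(Bin(12, *p*(1 − *q*)) ≥ 6) with it.

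| *c* | *q* | *p* = 0.40: without → with | *p* = 0.50: without → with |
|---|---|---|---|
| 0.9 | 0.001 | 33.5% → 33.3% | 61.3% → 61.1% |
| 0.8 | 0.017 | 33.5% → 31.7% | 61.3% → 59.0% |
| 0.7 | 0.071 | 33.5% → 26.3% | 61.3% → 51.5% |
| 0.6 | 0.179 | 33.5% → 16.8% | 61.3% → 36.3% |

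For scale, inclusion criterion 10 requires evening reports on 10 of 14 days, or 10/14 = 71%. The 0.7 row is therefore roughly a population in which everyone sits at the entry minimum.

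**4. Correlated weeks.** With a beta-binomial (assumed correlation 0.4, *p* = 0.50), the rate is 53.3% at *q* = 0, 51.2% at 0.05, 48.9% at 0.10 and 43.3% at 0.20. At *q* = 0.10 the loss is 53.3 − 48.9 = 4.4 points, against 61.3 − 47.3 = 14.0 with independent weeks.

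**5. Effect on the between-arm difference.** With the same *q* = 0.10 in both arms and independent weeks:

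| Weekly *p*, two arms | Difference without rule | Difference with rule |
|---|---|---|
| 0.4 vs 0.5 | 27.8 points | 23.8 points |
| 0.5 vs 0.6 | 22.9 points | 24.3 points |
| 0.6 vs 0.7 | 12.0 points | 17.4 points |

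The difference narrows in the first case and widens in the other two. If *q* differs by arm (assumed 0.02 vs 0.10) with *p* = 0.50 in both, the rates are 58.5% and 47.3%: an 11.2-point difference with no true effect.

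**The case against.** The strongest reply is that this is a drafting slip, not a decision. The same paragraph of 7.8.9.4 describes a weekly responder by a criterion on change from baseline, which neither weekly-question endpoint has. With the narrower scope in 7.3 and the separate rule under Table 3-2, this suggests text carried over from the daily-symptom responders. That is plausible, and a deliberate choice to overwrite answers is not shown. The sentence nevertheless covers the two endpoints as written.

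The trigger may also be narrower than it looks. The wording is about entering information in the eDiary, not about having daily scores. Bowel movements and loperamide use are eDiary entries too, so a day without an evening report might still count. This stands: it lowers *q* and adds a further ambiguity. Similarly, weeks with sparse diaries will often lack the weekly answer as well and could not count as a response under either text.

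Three stronger readings are tempting and should not be drawn:

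- *That the SAP contradicts the protocol.* The protocol does not forbid a diary minimum for these endpoints; it states none. The accurate description is an undeclared addition.
- *That Tables 3-1 and 3-2 check different days.* Table 3-2 lists the days on which a question is answered. For Week 2 (Days 8 to 14 in Table 3-1), an answer on Day 11 recalls Days 5 to 11 and one on Day 17 recalls Days 11 to 17; each covers 4 days of that week, so Days 11 to 17 in Table 3-2 point to the same analysis week. (From the Week 9/10 boundary, Table 3-2 runs one day earlier than this rule implies, a separate and minor matter.)
- *That the treatment difference necessarily shrinks.* Step 5 of the working shows otherwise.

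**Conclusion.** The point holds as a scope error. Followed literally, SAP 7.8.9.4 turns a valid favourable weekly answer into non-response for Degree of Relief and Adequate Relief, beyond the scope in SAP 7.3, without a basis in the protocol definitions and without a declaration in Appendix 1.

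The direction for each arm's rate is certain: it can only fall. The size is probably small. A 2.3-point loss is about 0.023 × 92 = 2 patients per arm. Losses of 7 to 10 points would need daily completion near 70% throughout, and larger ones still poorer diaries. These figures rest on the assumed *p*, *c* and independence; no completion data are in the documents. The effect on the dose-placebo contrast has no fixed direction, and unequal diary completion between arms could produce a spurious one, so the rule cannot be defended simply as conservative.

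Severity is low. Two of many additional endpoints are touched, all tested without multiplicity adjustment.

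**What to change.** In SAP 7.8.9.4, limit the 4-day sentence to responders built from daily scores (pain, discomfort, bloating, cramping). For Degree of Relief and Adequate Relief, define the weekly status by the answer assigned under Appendix Table 3-2, and count a week as non-response only if that answer is missing or the week follows treatment discontinuation.

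If the sponsor does want a diary-day minimum for these two endpoints, it should say which eDiary entries count towards it, and list and justify the change in Appendix 1.

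The cost is one sentence in the SAP and slightly simpler programming. No new data are needed, and nothing changes for the key endpoints or the sample size.
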